#### **9.9.4 ELECTROCARDIOGRAM (ECG)**

The number and percentage of patients with worst ECG result as ordered: abnormal, clinically significant; abnormal, not clinically significant; and Normal. Results will be summarized by treatment at scheduled visits. Results will be counted once for each patient and scheduled visit.

Descriptive summaries of observed and change from baseline values will be presented for ECG measures of HR, PR interval, QRS duration, QT interval, and QTc interval by scheduled visit. QTc interval is derived using Fridericia's correction method. These summaries will be presented by scheduled visit.

For QT interval corrected the following formulas should be used if not entered in the eCRF: Fridericia's correction : QTc = QT/(RR^3) and Bazett's correction, QTc = QT /SQRT(RR). The number and percentage of subjects having the following notable ECG interval values on treatment will be summarized as follows to evaluate risk of prolongation of QTc interval [as per the definition of International Conference on Harmonization (ICH, 2005)]:

- Maximum QTc intervals > 450 milliseconds, > 480 milliseconds, and > 500 milliseconds.
- Maximum changes from baseline in QTc > 30 and > 60.

ECGs will also be presented in a data listing.

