8.10.2. Retention of Samples

If allowable by local guidelines and/or policies, all blood, PBMCs, and tumor tissue samples will be retained for potential additional testing at a later date or to enable development of a companion diagnostic that would help to identify subjects most likely to benefit from JTX-2011 in the future.

Samples will be retained at a secure storage facility (to be selected, qualified, and contracted by Jounce Therapeutics) in case there is need for retesting. At the end of ten (10) years (or some other period based on local guidelines and/or policies), or if Jounce no longer requires the samples, they will be destroyed. Analyses may be conducted by Jounce Therapeutics, Inc. or by a designated lab at their discretion.

Biospecimens will not be labeled with any personal identifiers (e.g., date of birth, initials). They will be labeled with the subject's study number to allow for future exploratory research analyses to be correlated to the study data and treatment/dose assignments.

8.11. 12-Lead ECG

ECGs will be analyzed locally and data must be reported in the eCRF.

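### SAP 9.9.4 prints Fridericia's correction with RR cubed instead of its cube root, so any QTc derived from the printed formula would be wrong unless the heart rate is exactly 60 bpm

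*SAP*

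**What the plan says.** SAP 9.9.4 names the method: "QTc interval is derived using Fridericia's correction method". It then supplies formulas for a limited case: "the following formulas should be used if not entered in the eCRF: Fridericia's correction : QTc = QT/(RR 3", with the 3 set as a superscript on RR. The second formula, in the same sentence, is "Bazett's correction, QTc = QT /SQRT(RR", which is correctly a root. No unit is given for RR, and no other part of either document prints a cube-root version.

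QTc then feeds two sets of counts intended to show the risk of QTc prolongation: "Maximum QTc intervals > 450 milliseconds, > 480 milliseconds, and > 500 milliseconds" and "Maximum changes from baseline in QTc > 30 and > 60". Neither line says which correction it uses, and the second gives no unit (milliseconds are implied).

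On the source of the data, Protocol 8.11 says only that "ECGs will be analyzed locally and data must be reported in the eCRF". It does not say whether sites enter a QTc or only the measurements behind it.

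**The concern.** The section contradicts itself. It names Fridericia's correction and then prints a different operation. Cubing RR and taking its cube root move the result in the same direction but by very different amounts, so the error is not a matter of rounding or convention. Bazett's formula, printed beside it as a root, shows the form that was presumably intended.

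Safety is a primary objective in both phases of this first-in-human trial, and ECGs are a listed safety endpoint. If a derived QTc followed the printed formula, subjects with ordinary heart rates could appear in the prolongation counts, and real prolongation at slow rates could disappear from them. The second error is the harder to notice, because the values look low rather than absurd.

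**Working it through.** **Inputs from the documents**
- Printed formula: QT/RR^3 (SAP 9.9.4).
- Named method: Fridericia, that is QT/RR^(1/3) (SAP 9.9.4).
- Thresholds: 450, 480 and 500 ms; changes of 30 and 60 (SAP 9.9.4).
- Normal pulse range used by the SAP: 60 to 100 bpm (SAP 9.9.3, Table 8).

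**Assumptions not in the documents**
- RR in seconds, so RR = 60/HR.
- Illustrative true QTcF of 360 to 440 ms, and an illustrative raw QT of 380 ms.

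The plan states no QTc result, so there is no figure of its own to reproduce.

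**Step 1. Relation between printed and true values.** Put QT = QTcF × RR^(1/3) into QT/RR^3:

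printed value = QTcF × RR^(1/3 − 3) = QTcF × (HR/60)^(8/3).

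The two agree only at 60 bpm.

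**Step 2. Direct check with QT = 380 ms**

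| HR (bpm) | RR (s) | RR^3 | RR^(1/3) | Printed (ms) | Correct (ms) |
|---|---|---|---|---|---|
| 50 | 1.200 | 1.728 | 1.063 | 220 | 358 |
| 75 | 0.800 | 0.512 | 0.928 | 742 | 409 |
| 90 | 0.667 | 0.296 | 0.874 | 1283 | 435 |

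**Step 3. One subject with a constant true QTcF of 400 ms.** The printed formula gives 246 ms at 50 bpm, 400 at 60, 516 at 66, 603 at 70, 725 at 75, 861 at 80 and 1562 at 100. The correct formula gives 400 throughout.

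**Step 4. Heart rate at which the printed value passes 500 ms.** Solve QTcF × (HR/60)^(8/3) = 500, giving HR = 60 × (500/QTcF)^(3/8):

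| True QTcF (ms) | 360 | 380 | 400 | 420 | 440 |
|---|---|---|---|---|---|
| HR (bpm) | 67.9 | 66.5 | 65.2 | 64.1 | 63.0 |

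These rates lie in the lower part of the SAP's own normal pulse range. At 70 bpm, any true QTcF above 331.5 ms would be counted as above 500 ms.

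**Step 5. Slow heart rates.** At 50 bpm the multiplier is (50/60)^(8/3) ≈ 0.615. True values of 450, 480 and 500 ms become 277, 295 and 307 ms. At 55 bpm they become 357, 381 and 396 ms. None would reach the 450 ms count.

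**Step 6. Change from baseline.** With true QTcF constant at 400 ms, a rise from 70 to 72 bpm gives +47 ms, and from 70 to 75 bpm gives +122 ms. The true change is zero. From 70 bpm, about 1.3 bpm is enough to exceed +30 ms and about 2.5 bpm to exceed +60 ms. With raw QT constant at 380 ms, 70 to 80 bpm gives 900.7 − 603.4 = +297 ms, against a correct change of about +18 ms.

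**Step 7. The unit.** With RR in milliseconds the printed formula gives 380/800^3 ≈ 0.0000007. Even the correct root gives 380/800^(1/3) ≈ 41 ms. The unit therefore has to be stated alongside the corrected formula.

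**The case against.** **The exponent may be a reading artefact.** The SAP text used here was read from PDF, and a 1/3 exponent or a root sign could have been reduced to a 3. This is possible but not shown. The same SAP text kept the 1/2 subscript on the half-life symbol in its abbreviations list and the −1 superscript on days in its PK parameter table (8.2.1). The source page should be checked first.

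**A reader might infer that most subjects with a heart rate above about 66 bpm would be reported with QTc above 500 ms.** The documents do not support that. The formula applies only where QTc is not entered in the eCRF. That share is not stated and could be none. The rate of 66 bpm also depends on RR in seconds and on an assumed QT or QTcF; across plausible values it ranges from about 63 to 68.

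**A reader might also infer that site-entered and derived values of different methods would be mixed in one column or in one subject's change from baseline.** That depends on an eCRF that is not in the documents. Listing both Fridericia and Bazett is equally consistent with separate fields for each.

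**The error might never reach a table.** A programmer has a named standard method to follow, and values of 742 or 1283 ms would probably be questioned. This lowers the likely harm. It does not make the printed rule correct, and the low values at slow heart rates are less conspicuous.

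**The tables are descriptive.** This stands. QTc is not part of the DLT definition (Protocol 6.3), and the SAP presents clinically significant ECG abnormality separately from QTc.

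**Conclusion.** The point holds as a specification error. SAP 9.9.4 names one correction and prints another, and nothing else in the documents repairs it. For values derived as printed, with RR in seconds, the error is a factor of (HR/60)^(8/3). A true QTcF of 360 to 440 ms passes 500 ms at about 68 to 63 bpm, and 500 ms at 50 bpm is shown as about 307 ms. The threshold and change counts would be wrong for those values.

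The number of values affected is unknown, so no share of subjects can be claimed. A transcription artefact remains possible until the source page is checked. The consequence is confined to descriptive QTc safety tables; efficacy results and DLT rules are untouched. It is a simple correction to make before the tables are programmed.

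**What to change.** Check the source page of SAP 9.9.4 for a lost root sign or a 1/3 exponent. If the page does print RR cubed, replace it with QTcF = QT/RR^(1/3). In either case, state that RR is in seconds (60/HR), and add a sentence saying that the 450/480/500 ms counts and the change counts use QTcF, with the changes in milliseconds.

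Deriving QTcF from QT and heart rate for every ECG, and showing any eCRF-entered QTc only in the listing, would guarantee a single method. That is an optional consistency step, not the correction of a demonstrated error. QT and heart rate are already summarised in this section, so it needs no additional type of measurement.

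The cost is one formula and one or two sentences, plus the renewed signatures that SAP section 2 requires for any update after sign-off.

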#### **9.9.5 PHYSICAL EXAMS**

Physical exam data will be presented in a data listing.

#### **9.9.6 EASTERN COOPERATIVE ONCOLOGY GROUP PERFORMANCE STATUS**

The Eastern Cooperative Oncology Group (ECOG) performance status measures on a scale of 0 (normal activity) to 5 (dead). Frequency and percent for each category per at timepoint will be presented. Data will be presented in subject listings.

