6.8. Withdrawal of Subjects

A subject is free to withdraw from treatment or from follow-up at any time for any reason without prejudice to their future medical care by the physician or at the institution. However, subjects who withdraw from treatment should be encouraged to return for the end-of-treatment visit, complete all safety assessments, and enter long-term follow-up. If a subject refuses to undergo the end-of-treatment procedures, the reason for refusal should be fully documented in the patient's electronic Case Report Form (eCRF). Subjects who withdraw from follow-up should not be followed for any of the visits and assessments described above.

The Investigator or Jounce may also withdraw the subject from treatment at any time in the interest of his or her safety. The primary reason for withdrawal must be recorded in the subject's medical record and on the withdrawal form in the eCRF. If a subject is withdrawn for more than one reason, each reason should be documented in the source document and the most medically significant reason should be entered on the eCRF.

The withdrawal of a subject from treatment should be discussed where possible with the Medical Monitor before the subject stops taking study drug. If study treatment is discontinued, the final evaluations will be performed as completely as possible.

The reason for termination, date of stopping study treatment and the total treatment period must be recorded in the eCRF and source documents.

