7.4. End of Treatment (All Parts)

At the end of treatment (within 28 days \pm 7 days after last dose of study drug):

- Physical examination.
- Vital signs.
- ECOG performance status.
- 12-lead ECG.
- Laboratory assessments including chemistry, hematology, coagulation, thyroid function, and urinalysis.
- Prostate cancer subjects in Parts E and F only:
 - PSA
- Blood samples for Target Engagement, PK/ADA/NAb (not required for Part C subjects receiving nivolumab or pembrolizumab post-progression).
- CT Scan for response assessment (unless performed within 9 weeks of End of Treatment visit [within 12 weeks for prostate cancer subjects]).
- Record concomitant medications.
- Adverse events assessment.

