9.1.1. Safety Endpoints

The following safety endpoints will be assessed:

- Incidence and severity of treatment-emergent adverse events;
- Incidence and severity of treatment-emergent changes in clinical laboratory values;
- Incidence of dose limiting toxicities;
- Incidence of anti-drug antibodies to JTX-2011 and/or nivolumab, ipilimumab, or pembrolizumab;
- Incidence of neutralizing antibodies to JTX-2011 and/or nivolumab, ipilimumab, or pembrolizumab;
- Incidence of decreases in ECOG performance status;
- Incidence of clinically significant changes in ECG measurements.

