### **3.2 STUDY ENDPOINTS**

#### **3.2.1 SAFETY ENDPOINTS**

Assessment of safety and tolerability are primary objectives for both Phase 1 parts (A, B, E, G) and Phase 2 parts (C, D). Safety evaluations will include safety data throughout the duration of the study from enrolment to 28 days after last dose of study treatment using all available data. Safety will be characterized by System Organ Class (SOC) and Preferred Term (PT), frequency, relatedness to study treatment and severity of adverse events as coded using the MedDRA version 19 coding system and graded by NCI Common Toxicity Criteria for Adverse Events NCI CTCAE version 4.03. Safety endpoints also include laboratory values, vital signs, ECGs and Eastern Cooperative Oncology Group (ECOG) performance status.

Additional safety endpoints are described in section 3.2.5.1 and details of analyses and presentation will be included in the exploratory statistical analysis plan (eSAP).

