## 7.12 MISSING DATA

### 7.12.1 IMPUTATION OF NON-DATE MISSING DATA FOR STATISTICAL ANALYSES

Unless otherwise explicitly specified, missing data will not be imputed. All available time to progression or death data will be analysed using appropriate statistical methods that allow for censoring when no progression or death is reported. Subjects with reported shorter treatment and/or follow-up intervals will not be considered to have missing time to progression or death status. Subjects with premature study withdrawal (including lost to follow-up) will be included in any analyses where they contribute data and where they conform to the analysis population of interest.

Subjects without baseline tumor assessments will be considered non-evaluable for ORR and irORR analysis.

When using RECIST v1.1 or irRC criteria to estimate the proportion of responders, all subjects in Response Evaluable Set will be included in the denominator even when their responses are missing.

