#### 9.9.2 LABORATORY DATA

Laboratory parameters will be analyzed using categorical summaries.

Categorical analysis of laboratory tests using observed data includes summarizing laboratory abnormalities considered clinically significant and treatment-emergent. The following defines this group;

- Abnormality satisfies current criteria and occurs first time while the patient is on study treatment (i.e., not seen prior to treatment).
- Abnormality satisfies the current criteria of abnormality, was observed prior to start of treatment, and worsened during study treatment.

The number of patients evaluable for laboratory abnormalities must have at least one observation for at least one test while on treatment. While the number of patients evaluable for clinically significant laboratory abnormalities (includes lab TEAEs) is the number of patients with a clinically significant abnormality for at least one laboratory test while on treatment.

Additional summaries will be produced overall by Maximum CTCAE grade. Frequencies and percentages in each grade and overall will be presented.

Shift in laboratory analyte grade will be characterized by worst on-study CTCAE grade to end of treatment. Shift categories from baseline will be selecting the maximum CTCAE grade for each patient during the study compared to baseline. Grades that are not part of CTCAE grading will be blank. Percentages will be based on the number of patients with non-missing baseline and postbaseline values per each analyte.

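### The protocol's ECOG safety endpoint is a per-subject incidence of decline, but the SAP's by-timepoint category frequencies cannot produce it

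*SAP*

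**What the plan says.** Protocol 9.1.1 (Safety Endpoints) includes "Incidence of decreases in ECOG performance status". It sets no threshold, reference value or time window.

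SAP 3.2.1 keeps ECOG among the safety endpoints: "Safety endpoints also include laboratory values, vital signs, ECGs and Eastern Cooperative Oncology Group (ECOG) performance status". It gives no derivation. SAP 9.9.6 then describes the 0 (normal) to 5 (dead) scale and plans two outputs: "Frequency and percent for each category per at timepoint will be presented" and "Data will be presented in subject listings". It states no denominator. SAP 9.2 tabulates baseline ECOG as a separate distribution.

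Three other provisions bear on who is counted at a timepoint:

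- Protocol 7.4 schedules "ECOG performance status" at End of Treatment in all parts, 28 ± 7 days after the last dose.
- Protocol 6.8 says that "subjects who withdraw from treatment should be encouraged to return for the end-of-treatment visit, complete all safety assessments, and enter long-term follow-up".
- SAP 7.12.1 says "Unless otherwise explicitly specified, missing data will not be imputed".

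**The concern.** An incidence of decline is a within-subject quantity. It needs each subject's baseline, that subject's later values, a rule for what counts as decline, and a single count per subject. A by-timepoint frequency table shows only how many subjects are in each grade on a given occasion, so improvement in some subjects can hide worsening in others. The composition of each row also changes as subjects leave.

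Safety is a primary objective in every part the SAP covers. As the plan stands, the study report could carry a full set of ECOG tables and still not state how many subjects declined. A reader wanting that number would have to count it by hand from the listings, using a definition that neither document supplies.

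**Working it through.** **1. Is the endpoint derived anywhere else in the SAP?** It is not.

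| SAP section | What it gives for ECOG |
|---|---|
| 3.2.1 | Names it as a safety endpoint |
| 3.2.5.1 | Exploratory safety list covers cytokines and lymphocyte subsets only |
| 7.2, 7.3 | General rules: frequencies for categorical data, and a definition of change from baseline that 9.9.6 does not call on |
| 8.1 | Defines adverse event endpoints only |
| 9.2 | Baseline distribution on its own |
| 9.9.6 | Category frequencies by timepoint, and listings |

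Other safety measures do get a per-subject summary. For laboratory grades, "Shift categories from baseline will be selecting the maximum CTCAE grade for each patient during the study compared to baseline". SAP 9.9.4 counts subjects by maximum change from baseline in QTc, and SAP 9.10.2 counts each ADA- or NAb-positive subject once.

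**2. Can the endpoint be recovered from the planned table with full attendance?** Take an illustrative cohort of 15, the approximate Part C and D cohort size, with grades 0 and 1 only (Protocol 4.1 admits grades 0-1, and grade 2 by approval in the Phase 2 parts). Suppose 8 subjects are at grade 0 and 7 at grade 1 at baseline, with the same split at a later visit.

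- Fewest who worsened: nobody changed, 0/15 = 0%.
- Most who worsened: min(8 at grade 0 at baseline, 7 at grade 1 later) = 7. Seven move from 0 to 1 and seven from 1 to 0, leaving 1 + 7 = 8 at grade 0 and 7 at grade 1. That is 7/15 = 47%.

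Both histories give the same table. The End of Treatment row has the same limitation, because it is not linked to baseline either.

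**3. What does dropout add?** The documents state no ECOG worsening rate and no dropout rate, so every rate below is an assumption. The comparison is generous to the plan, because it supposes the by-visit percentage worse than baseline were available, which SAP 9.9.6 does not produce. Let p be the per-cycle chance of worsening, over 8 cycles.

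- *No dropout, no recovery, p = 8%.* Ever worsened = 1 − 0.92^8 = 48.7%. The last visit also shows 48.7%. Ratio 1.00.
- *Dropout of 10% per cycle unrelated to ECOG, no recovery, p = 8%.* Ever worsened while on study = 0.08 × (1 − 0.828^8)/(1 − 0.828) = 36.2%, where 0.828 = 0.92 × 0.90. The last visit shows 48.7% of those remaining. Ratio 1.34, an overstatement.
- *Selective dropout, 10% recovery per cycle* (simulation, 100,000 subjects, 90% attendance at End of Treatment):

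| p | Leaving per cycle: worsened / not | Ever worsened | Highest on-treatment row | Ratio | End of Treatment row |
|---|---|---|---|---|---|
| 8% | 30% / 15% | 31.4% | 22.1% | 0.70 | 28.6% |
| 8% | 50% / 15% | 31.6% | 10.5% | 0.33 | 33.2% |
| 15% | 50% / 20% | 44.5% | 23.0% | 0.52 | 43.3% |
| 8% | 80% / 15% | 31.3% | 2.6% | 0.08 | 35.6% |

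Across all the rates tried (p 8-15%, recovery 0-30%, leaving 0-80% if worsened and 0-20% if not, End of Treatment attendance 50-100%), the ratio for on-treatment rows ran from 0.08 to 1.34. Where worsened subjects left faster, the End of Treatment row was 0.91 to 1.14 of the ever-worsened incidence. In these runs attendance at that visit did not depend on ECOG.

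**The case against.** The strongest reply is that this is a traceability gap with little consequence. The SAP tests no hypothesis (3.3.1) and summarizes safety descriptively (9.9). Baseline ECOG is tabulated and every later value is listed. The Safety Monitoring Committee sees ECOG directly in its dose-escalation reviews (Protocol 6.1.1), and new or increasing symptoms of progression are reported as adverse events (Protocol 8.14.1). All of this stands, and it limits the importance of the point. It does not supply the missing analysis: a listing is not an incidence, and none of these provisions says who counts as having declined.

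A reader might go further and infer four things that the documents do not support:

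- *That decline will be understated by about half.* No rate in either document leads to that figure. It appears only under particular assumed rates, and others give no shortfall or an overstatement. The SAP also never presents a by-visit percentage as the incidence.
- *That subjects who worsen and leave are lost.* ECOG is scheduled at End of Treatment in all parts, and 9.9.6 does not exclude that visit. These subjects appear there if they attend.
- *That the omission cannot have been deliberate because laboratory grades get a shift table.* The SAP treats safety domains at different depths (physical exams are only listed), so a lighter ECOG summary could have been chosen.
- *That the protocol names the wrong direction.* A decrease in performance status ordinarily means worse function. The wording is ambiguous only because the score rises as function falls.

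**Conclusion.** The point holds as a mismatch between endpoint and analysis. The protocol asks for a per-subject incidence of decline, and the SAP plans marginal frequencies from which it cannot be obtained. That conclusion follows from the two texts and needs no assumption about dropout. In the 15-subject illustration, one and the same table is compatible with 0% to 47% of subjects having worsened.

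Selective dropout is a secondary caution for the on-treatment rows. Its size and direction cannot be determined from the documents, and the End of Treatment row offsets it to the extent that leavers attend. The priority is low: the endpoint is descriptive and no dose or efficacy rule in the SAP depends on it.

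**What to change.** Add to SAP 9.9.6:

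- A shift table from baseline (as defined in SAP 7.3) to worst post-baseline ECOG, including End of Treatment and unscheduled visits, by part and by dose level or cohort.
- The number and percent of Safety Analysis Set subjects with an increase of at least 1 point and of at least 2 points, each subject counted once.
- The number of subjects with no post-baseline ECOG, shown alongside.
- A sentence stating that a decrease in performance status means an increase in ECOG score.

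The by-timepoint table can stay as a supplement. The cost is one additional table and a short definition, from data already collected. SAP section 2 allows updates with further signature and approval.
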